6.3. Sample Size Considerations

6.3.1. Sample Size

102 healthy controls

6.3.2. Sample Size Calculation

The exact sample size calculation is difficult due to several problems – there is very limited data about spinal cord volume in both MS patients and HC. In addition to that spinal cord volume is scanner and protocol specific, so it is not possible to use directly data from other centres.

Based on current knowledge we can estimate that MS patients are losing spinal cord volume 3-5 times faster compare to HC. The problem is that this can be age and sex specific and different in different MS phenotypes. So, it is reasonable to choose the group of HC that the best copy a typical MS patient population, i.e. ratio of male : female 1:2 and age range 18-60 years.

From the statistical point of view is generally recommended to have at least 10 subjects in each age and sex specific subgroup (see Table 1). Taking into account that the study is planned for 4 years and there is a risk of drop out of some participants we recommend to increase number of participants in each group by 2.

Based on this conditions we recommend to enrol:

Table 1.

Age range / Sex	Male	Female
18-30 years	12	22
30-40 years	12	22
40-60 years	12	22
Total	36	66

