- Description of results of different normalisation strategies, using different variables, e.g. sex, age, body height, height of C3 vertebra (or other vertebra

derived metrics), total intracranial volume (TIV).

- Description of absolute and normalised spinal cord volume and its variability in predefined spinal segments in different age and sex groups of HC.
- Description of absolute and normalised brain volumes in HC measuring whole brain, TIV and different regional brain volumes, especially – gray and white matter compartment, corpus callosum, thalamus, and cerebellum.

Tertiary Endpoints

- Correlation between spinal cord volume (total and GM, WM separately) and several brain metrics (total brain volume, GM, WM, lateral ventricles, thalamus, corpus callosum, brainstem and cerebellum) in HC.
- Comparison of results from different MRI protocols

Study Design:	Prospective, longitudinal, monocentric, interventional study
Study Location:	Czech Republic
Number of Planned Subjects:	102 subjects – intended as healthy controls (HC) from general population
Study Population:	This study is conducted in healthy subjects. Detailed criteria are described in the protocol.
Statistical Methods:	Binary or categorical variables will be presented as frequency distributions. Continuous variables will be reported by summary statistics: mean and standard deviation (SD) or median and range. The relationship between age and spinal cord volume will be determined separately for female and male patients in different decades to determine sex- and age-related effects on spinal cord volume. The spinal cord volume (and eventually also spinal cord gray- and white matter volumes) will be compared in three age-specific groups: 18-30 years, 30-40 years and 40-60

CONFIDENTIAL

years.

Annualised change of spinal cord volume will be calculated for each participant as the slope of a regression line fitted to all four timepoints (M0, 12, 24 and 36) with the assumption of linear change over time for each participant and for all participant (in a decade-specific manner) together.

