4. STUDY POPULATION

4.1. Inclusion Criteria

To be eligible to participate in this study, subject must fulfil the following eligibility criteria:

1. Each participant must provide informed consent in accordance with local regulations
2. Age 18-60 years.

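### Table 1's single 40-60 row leaves coverage of ages 50-60 to chance, although decade-specific, sex-separate analysis and an age-matched comparison with MS patients are planned

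*Combined protocol and SAP*

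**What the plan says.** Section 4.1 has one age criterion: "Age 18-60 years". Section 3.2.1 describes recruitment through personal discussion and mentions no stratification. Section 6.3.2 states that "it is reasonable to choose the group of HC that the best copy a typical MS patient population" and gives the target as "ratio of male : female 1:2 and age range 18-60 years". It asks for "at least 10 subjects in each age and sex specific subgroup" and, to allow for dropout, would "increase number of participants in each group by 2". Table 1 then sets 12 men and 22 women in each of three bands: 18-30, 30-40 and 40-60 years.

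The Statistical Methods entry in the synopsis says that the relation of age to cord volume will be "determined separately for female and male patients in different decades". It names "three age-specific groups: 18-30 years, 30-40 years and 40-60" years as the groups to compare, and plans annualised change for all participants together "in a decade-specific manner". Section 2.2.1 says that the control data will be compared with age- and sex-matched MS patients. The primary endpoint (2.3.1) is a cut-off separating the two populations.

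**The concern.** Table 1 gives the same 34 people to bands 12, 10 and 20 years wide, so sampling is thinnest in the oldest band, and nothing spreads recruits within it. A site could fill the 40-60 cells mostly with people in their forties and still comply fully.

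That matters because the plan intends decade-specific results and a matched comparison over a range that runs to 60. With few controls aged 50 or over, the healthy values there rest on a fitted age curve whose shape cannot be checked at those ages. The gap would be hard to repair: section 2.1 says that the ranges are scanner-specific, section 6.3.2 says that other centres' data cannot be used directly, and section 3.2 closes enrolment after at most 12 months.

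**Working it through.** **1. The plan's own figure.** Men: 3 × (10 + 2) = 36. Women: 3 × (20 + 2) = 66, where 20 = 2 × 10 from the 1:2 ratio. The total is 102, as in Table 1. This is a rule of thumb; the plan states no alpha, power, effect size or SD.

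**2. Sampling density.** 34/12 = 2.8, 34/10 = 3.4 and 34/20 = 1.7 people per year of age in the three bands.

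**3. How many would be aged 50 or over.** The documents do not give the share p of 40-60 recruits aged 50 or over, so it is an assumption, shown over a range. Counts are taken as Binomial(12, p) for men and Binomial(22, p) for women.

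| p | Expected men | P(men ≤ 3) | P(men ≤ 1) | P(no men) | Expected women | P(women ≤ 3) |
|---|---|---|---|---|---|---|
| 0.5 (even ages) | 6.0 | 7% | 0.3% | 0.02% | 11.0 | 0.04% |
| 0.4 | 4.8 | 23% | 2.0% | 0.2% | 8.8 | 0.8% |
| 0.3 | 3.6 | 49% | 8.5% | 1.4% | 6.6 | 7% |
| 0.2 | 2.4 | 80% (0.795) | 27% | 7% | 4.4 | 33% |

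The exposure is mainly in men. Even with p = 0.5, the chance that at least 10 of the 12 men are aged 50 or over is 1.9%, so the plan's minimum of 10 is out of reach for men in that decade.

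**4. Effect on precision at age 55.** Take the 36 men, with 12 ages evenly spaced over 18-30, 12 over 30-40, 12 − k over 40-50 and k over 50-60. With X the design matrix in age and x the row for age 55, the standard error of the fitted mean in residual-SD units is SE = √(x′(X′X)⁻¹x). The SD for predicting one new man is √(1 + SE²).

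| Men aged 50-60 (k) | SE, linear age | SE, quadratic age | Predictive SD, linear | Predictive SD, quadratic |
|---|---|---|---|---|
| 6 | 0.32 | 0.37 | 1.05 | 1.07 |
| 3 | 0.36 | 0.48 | 1.06 | 1.11 |
| 1 | 0.39 | 0.67 | 1.07 | 1.20 |

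The mean age of the 12 men falls from 50.0 (k = 6) to (9 × 45 + 3 × 55)/12 = 47.5 (k = 3).

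Pooling all 102 participants with an additive sex term softens this. For 6 men and 11 women against 3 men and 6 women aged 50-60, the SE for a man of 55 is 0.23 against 0.25 (linear) and 0.26 against 0.31 (quadratic). The plan specifies neither the form of the age effect nor pooling, and the synopsis speaks of analysis by sex.

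**5. Sizing a split.** Halving the row gives 12/2 = 6 men and 22/2 = 11 women per decade. Applying the plan's 12/22 rule to both decades would need 4 × (12 + 22) = 136 people, 34 more than planned.

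**The case against.** A reader might infer that the 50-60 range will be almost empty. The documents do not support that. They say nothing about volunteers clustering in the early forties, and even ages would give about 6 men and 11 women, the same as the proposed sub-quotas. At a 30% share, one man or none aged 50 or over has probability 8.5%, and none 1.4%. Three men are few, but not none.

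A reader might also infer that the cut-off will be biased, with ordinary ageing counted as pathology. That follows only if MS patients in their fifties are compared with younger controls. Section 2.2.1 promises an age-matched comparison. If patients are drawn from a large pool (section 2 reports 1,036 already assessed) to match the ages of the controls, the mismatch does not arise. The synopsis and section 2.1 describe the controls as the matched group, so the direction of matching is unclear.

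Thirdly, the documents nowhere name a 50-60 reference range. The synopsis refers to decades but then lists three groups ending in 40-60, so the word may be a loose label for those groups. Resemblance to MS patients is specified only by sex ratio and overall age range.

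Finally, participants enrolled at 47-49 reach 50 by month 36 and contribute some later scans, and an individual cut-off depends mostly on residual SD, which dominates the predictive SD in all but the sparsest case. These points limit the size of the problem. They do not supply any rule that secures coverage of the upper decade.

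**Conclusion.** The point holds as an uncontrolled recruitment risk. No text requires anyone aged 50-60, while the synopsis plans sex-separate, decade-specific results and the matched comparison covers ages up to 60.

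Its size depends on the assumed share aged 50 or over: the chance of 3 or fewer men runs from 7% at 50% to 80% at 20%. The precision cost of having 3 men rather than 6 is small if age is linear and moderate if it is curved. It becomes marked only with about 1 man and a curved relation (SE 0.67). These standard errors assume men analysed alone and ages evenly spread within each segment. Bias is conditional on how MS patients are matched and should not be asserted. The change is worth making because it costs almost nothing and cannot be made once enrolment closes.

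**What to change.** Keep 102 participants and every Table 1 total. Split the 40-60 row into enrolment sub-quotas of about 6 men and 11 women for each of 40-49 and 50-60. If the ages of the site's MS cohort are known, set the split in proportion to them; an even split is not shown to resemble that cohort. Add to section 4.1 that a volunteer is enrolled only while the relevant age-sex cell is open.

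State that the sub-quotas secure age coverage within the 40-60 group and are not stand-alone subgroups, because 6 men is below the plan's own minimum of 10 even before dropout. Limit decade-specific claims for 50-60 accordingly, and say in the synopsis whether decades means calendar decades or the three named groups.

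The cost is one table row and a few sentences, with no extra participants or scans. The downside is slightly slower recruitment of the last older volunteers within the 12-month enrolment window.

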7. ETHICAL REQUIREMENTS

The Investigators complies with all instructions, regulations, and agreements in this protocol and International Conference on Harmonisation (ICH) and Good Clinical Practice (GCP) guidelines if applicable.

7.1. Ethics Committee

Participating investigators must obtain ethics committee (EC) approval of the protocol, informed consent form (ICF), and other required study documents prior to starting the study if applicable.

It is the responsibility of the Principal Investigator to ensure that all aspects of institutional review are conducted in accordance with current governmental regulations.

7.2. Subject Information and Consent

Participant consent prior to performing any study-related activities will be obtained in accordance with local regulations.

7.3. Subject Data Protection

EC and various government health agencies may inspect the records of this study. Every effort will be made to keep the subject's personal medical data confidential.

In any presentations or in publications of the study results, the participants' identities will remain anonymous and thus confidential. The participant will not be identified by name in the database or in any study reports.

8. ADMINISTRATIVE PROCEDURES

8.1. Quality Assurance

The investigators will be expected to cooperate with any audit and to provide assistance and documentation (including source data) as requested.

8.2. Publications

Scientific findings of the data analysis will be published in line with ICMJE guidelines. Roche financial support will be transparently acknowledged. Publication plan will be in details described in the contract agreement.

9. FURTHER REQUIREMENTS AND GENERAL INFORMATION

9.1. Changes to Final Study Protocol

All protocol amendments must be submitted to the EC and Regulatory Authorities if required by local law.

In the event of a protocol modification, the subject ICF may require similar modifications.

9.2. Ethics Committee Notification of Study Completion or Termination

Where required, the Health Authorities and EC must be notified of completion or termination of this study, and sent a copy of the study synopsis in accordance with necessary timelines.

9.3. Retention of Study Data

[figure not shown]
The minimum retention time for study records will meet the strictest standard applicable to that site, as dictated by any institutional requirements or local laws or regulations.

